4.12. Subject Replacement

Subjects who discontinue study therapy prior to completing Cycle 1 (Day 28) for reasons other than the development of a DLT will be replaced. Subjects who miss one or more doses for reasons other than DLT, must receive at least 75% of the total planned voruciclib dose in Cycle 1 to be assessed for DLT. Subjects with no DLT who fail to receive at least 75% of the planned Cycle 1 voruciclib dose will be replaced.

For Cohort 12, subjects must receive 100% of Cycle 1 doses (i.e., all 6 doses) to be DLT evaluable; subjects with no DLT who fail to receive 100% of Cycle 1 voruciclib doses will be replaced.

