If a subject experiences an AE, appropriate supportive care (e.g., antiemetics, antidiarrheals, antibiotics, granulocyte colony-stimulating factor [G-CSF] hydration) should be instituted consistent with the nature of the event. If the AE requires a dosing modification, the treatment regimen should be interrupted, as necessary. A decision should be made as to whether the subject can reasonably continue with the study drug based upon the nature and severity of the AE.

Recommendations regarding specific types of concomitant therapies, supportive care, diet, and other interventions are provided below. To minimize variations in supportive care, the recommended supportive care agents (e.g., loperamide, granisetron) should be used unless there is a medical rationale in a specific subject for use of an alternative product.

Antibiotics, Antifungals, Antivirals

Care should be taken to avoid or minimize concomitant administration of prophylactic or therapeutic antibacterial, antifungal, or antiviral agents that are moderate or strong CYP3A4 inhibitors or inducers. For subjects with CLL/SLL and a history of recurrent infections, prophylaxis with intravenous immunoglobulin may be offered and consideration may be given to initiation of antibiotic prophylaxis against pneumocystis infection (e.g., with trimethoprim-sulfamethoxazole, dapsone, aerosolized pentamidine, or atovaquone) beginning prior to study drug administration. Such support also offers the benefit of reducing the risk for other bacterial infections. Local practices or guidelines regarding infection prophylaxis may be followed.

Subjects developing an intercurrent infection during study drug treatment may receive therapeutic antibacterial, antiviral, or antifungal drugs for intercurrent infections as needed. Continuation of study therapy during treatment for an intercurrent infection is at the discretion of the Investigator. Given that voruciclib is a CYP3A4 substrate and the critical role of azole antifungals (commonly strong CYP3A4 inhibitors) in the treatment of fungal infections in patients with AML, voruciclib must be held during treatment with an azole and restarted when the azole therapy is completed. Antifungals other than azoles may be used if considered by the investigator as a clinically appropriate alternative to azoles.

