For the combination cohorts on IS_{2w,2w} (Amendment 11), the starting dose of voruciclib in Cohort 12 is 50 mg QOD, which will further reduce voruciclib exposure to account for potential increases (if any) in bioavailability of the new malonate tablet formulation during the exposure cycles. Dosing in Cohort 13 (50 mg QD) will commence only after the safety of QOD dosing of voruciclib with venetoclax in Cohort 12 is established.

For the first two dose levels (50 mg QOD and 50 mg QD), for which voruciclib dose reduction is not possible, voruciclib will be temporarily stopped if the subject requires treatment with an azole antifungal due to the potential of drug-drug interactions and increase exposure to voruciclib. Subjects who recover from the infection can restart voruciclib after the last dose of the azole antifungal (after at least 5 times the half-life of the agent). For subjects receiving

voruciclib at or above 100 mg, a dose reduction by 1 dose level will be required for concomitant treatment with an azole or other strong CYP3A4 inhibitor.

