Cycle	Day	Time of Collection	
		Pre-dose	Post-dose
1	14	X	2, 4, 6 and 8-hours
	15	X (approximately 24 hours after Day 14 dose)	-
	21	anytime during clinic visit	
2	1	X	2, 4 and 6-hours post-dose of venetoclax (voruciclib to be dosed 6 hours after venetoclax administration, after completion of the 6- hour sample collection)
4, 6	1, 14 (± 3 days)	anytime during clinic visit	
Every 3 cycles thereafter	1, 14 (± 3 days)	anytime during clinic visit	

DDI Assessment: Venetoclax exposure (when co-administered with voruciclib) will be compared to historical single agent data to assess DDI and the effect of voruciclib on venetoclax pharmacokinetics. Venetoclax concentrations on Cycle 2 Day 1 and Cycle 1 Day 14 will also be compared assuming limited effect, if any, on voruciclib on Cycle 2 Day 1.

Voruciclib PK and other relevant data from all clinical trials (including late phase clinical trials) will be pooled and analyzed using population PK methods. Additionally, voruciclib exposure-response and exposure-safety assessments will be performed and the results will be presented in a separate report.

PK of voruciclib in subjects receiving co-administered azole antifungals versus those without azole antifungals will be compared.

Detailed instructions on collection of plasma for determination of voruciclib and venetoclax will be provided in the Site Laboratory Manual.

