10.3.2. Analysis Populations

The Safety population is defined as subjects who receive at least one dose of study drug(s).

The DLT evaluable population includes subjects in dose escalation cohorts who complete the first cycle of treatment with at least 75% of study drug compliance or experience a DLT during the first cycle (28 days) of treatment.

The Efficacy evaluable population is defined as subjects who complete the first scheduled post-baseline efficacy evaluation (scheduled on C3D1 for B-cell lymphoma subjects and C2D1 for AML subjects) or develop progression of disease or death prior to the first scheduled post-baseline efficacy.

The PK population will include all subjects who receive at least 1 dose of voruciclib or venetoclax and have at least 1 non-missing post-dose concentration value.

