### **6.2 DLT Evaluable Set**

The DLT Evaluable Set will comprise all subjects in the Safety Evaluable Set who completed the first cycle of treatment (defined as taking at least 75% of the prescribed dose during Cycle 1; for Cohort 12, subjects must receive 100% of Cycle 1 doses (i.e., all 6 doses)) or experienced a DLT during the first cycle of treatment. Subjects who discontinue study therapy prior to completing Cycle 1 (Day 28) for reasons other than the development of a DLT will be replaced. Also, subjects with no DLT who fail to take at least 75% of the planned Cycle 1 voruciclib dose will be replaced; for Cohort 12, subjects with no DLT who fail to receive 100% of Cycle 1 voruciclib doses will be replaced.

The DLT rate will be computed based on subjects in the DLT Evaluable Set.

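### Conflicting voruciclib rules for azole treatment (4.14.1 against 4.15) and for confirmed Grade 2 pneumonitis (4.11 text against Table 12) can change how a Cycle 1 subject counts in the 3+3

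*Protocol*

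**What the plan says.** **Azoles.** Protocol 4.14.1 gives one instruction for AML patients who need an azole: "voruciclib must be held during treatment with an azole and restarted when the azole therapy is completed". It makes no exception by dose or cohort. Section 4.15, writing about the combination portion, stops voruciclib in a narrower setting: "For the first two dose levels (50 mg QOD and 50 mg QD), for which voruciclib dose reduction is not possible". From 100 mg upward it says that "a dose reduction by 1 dose level will be required for concomitant treatment with an azole or other strong CYP3A4 inhibitor". The restart points also differ: the end of azole therapy in 4.14.1, and at least five azole half-lives after the last dose in 4.15 (for the 50 mg levels). Section 9.14.2 then plans that "PK of voruciclib in subjects receiving co-administered azole antifungals versus those without azole antifungals will be compared".

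**Pneumonitis.** The text of 4.11 has voruciclib suspended on suspicion and stopped for good on confirmation, at any grade. Table 12, cited in the same paragraph, asks at Grade 2 for a hold until Grade 1 or lower. It lists permanent discontinuation only at Grade 3 or 4.

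**Counting.** Under Protocol 4.12, "Subjects with no DLT who fail to receive at least 75% of the planned Cycle 1 voruciclib dose will be replaced". The DLT-evaluable definitions use other words: Protocol 10.3.2 has subjects who "complete the first cycle of treatment with at least 75% of study drug compliance", and SAP 6.2 has completion "defined as taking at least 75% of the prescribed dose during Cycle 1". Under 4.4, a nonhematological event outside the specific criteria is a DLT only at Grade 3 or higher. Discontinuing study drug in Cycle 1 for an adverse event clearly unrelated to the disease or an extraneous cause is also a DLT.

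**The concern.** Each pair gives a site two different instructions for the same patient, and nothing says which prevails. A site that reduces the dose under 4.15 departs from 4.14.1. A site that holds under 4.14.1 does not give the co-administration that 4.15 and 9.14.2 provide for.

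Two things are at stake. One is exposure: whether voruciclib continues alongside a strong CYP3A4 inhibitor, and whether a subject with confirmed Grade 2 pneumonitis is re-exposed. Pneumonitis or ILD was the DLT in 2 of the 4 AML subjects at 100 mg continuous dosing (4.2.1.1), both with confounding factors (4.11). The other is the primary endpoint: in Cycle 1 the choice of rule can move a subject between evaluable and replaced (azoles), or between DLT and no DLT (pneumonitis).

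**Working it through.** No stated sample size or error rate depends on this point, so the check is dose counting against the 75% rule.

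**Inputs**
- Planned Cycle 1 doses N. Table 5, Days 3–14: 14 − 3 + 1 = 12. Table 6, Days 3–21: 21 − 3 + 1 = 19. As a check, the same counting gives 6 doses for Cohort 12 (Days 3, 5, 7, 9, 11, 13), the number stated in 4.12.
- Dose step: 50 mg (Tables 3 and 4).
- Threshold: 75% of planned milligrams (4.12).
- k = Cycle 1 dosing days on an azole. This is not documented, so it is shown over its range, for a subject with no DLT and no other missed dose.
- Open cohorts: 18–19 and 21–25. Section 4.3.2 reports no DLTs on IS2w,2w through 250 mg and enrollment under way at 300 mg.

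**Hold: share received = (N − k)/N**
- IS2w,2w: k = 3 gives 9/12 = 75%; k = 4 gives 8/12 = 67%, replaced.
- IS3w,1w: k = 4 gives 15/19 = 79%; k = 5 gives 14/19 = 74%, replaced.

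**Reduce one level: share received = 1 − (k/N)(50/dose)**
- Every dose reduced (k = N): 200 mg 75%, 250 mg 80%, 300 mg 83%, 350 mg 86%. The subject stays evaluable at every k.
- Cohort 21, 150 to 100 mg: k = 14 gives 1 − 14/57 = 75.4%; k = 15 gives 1 − 15/57 = 73.7%, replaced.

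The two rules therefore classify the same subject differently for k = 4 to 12 in Cohorts 18–19, k = 5 to 19 in Cohorts 22–25, and k = 5 to 14 in Cohort 21. With an assumed 7 azole days, Cohort 18 receives 5/12 = 42% under hold and 1 − (7/12)(50/300) = 90% under reduction. Cohort 21 receives 12/19 = 63% and 1 − 7/57 = 88%.

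**Other readings of 75%.** If compliance or prescribed dose means the dose prescribed after reduction, the reduced subject is at 100% for every k. If held doses also count as not prescribed, both rules leave the subject in the DLT set, yet 4.12 still replaces the held subject.

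**Grade 2 pneumonitis in Cycle 1, clearly unrelated to disease or an extraneous cause**
- 4.11 text: permanent discontinuation, hence a DLT under 4.4.
- Table 12 with hold and restart: no DLT. The subject is evaluable if at most 3 of 12 or 4 of 19 doses are missed, otherwise replaced. To illustrate with Table 12's 3-day checks and enough dosing days left: 3 missed doses give 9/12 = 75% or 16/19 = 84%; 6 missed give 6/12 = 50% or 13/19 = 68%.
- One DLT turns 0/3 into 1/3 (expand the cohort) or 1/6 into 2/6 (no escalation).

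**Illustration with assumed rates.** The chance of passing a cohort with DLT rate p is (1 − p)³ + 3p(1 − p)⁵. Suppose other DLTs occur in 20% of subjects and such Grade 2 cases in a further 5% to 10%. The chance is 0.71 if the Grade 2 cases count as evaluable without a DLT, and 0.60 to 0.49 if they count as DLTs. With 10% other DLTs it is 0.91 against 0.81 to 0.71.

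**The case against.** **4.15 is the more specific rule, and holding does not strictly breach it.** Its reduction applies to concomitant treatment, and a held dose is not concomitant. This stands in part: only the site that reduces breaches explicit wording. But 4.14.1 is mandatory, is about AML, and is followed directly by a paragraph on the combination groups that exempts nobody. Section 4.15 stops voruciclib at 50 mg because no reduction is possible there, which means stopping is not its rule higher up. The investigator discretion that 4.14.1 gives during intercurrent infection comes just before the specific azole instruction and does not soften it.

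**Table 12 never says to restart, and permanent discontinuation would not violate it.** True. But a hold with a recovery endpoint implies resumption, and the table keeps permanent discontinuation for the next row.

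**The SRC approves each escalation after reviewing all available safety data** (4.3.2), and replaced subjects remain in the safety set (SAP 3.1.4, 6.1). This stands, and it softens the counting consequence without removing it.

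**The setting is narrow.** Azole prophylaxis is excluded in the combination groups (4.14.1) and screening azoles are washed out (4.14.3), so the azole conflict needs a new therapeutic azole on dosing days. This also stands.

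Some stronger readings are tempting but unsupported:
- A reader might infer that the five-half-life wait alone pushes subjects in the open cohorts below 75%. That wait is written only for the 50 mg levels, and no azole half-life is given.
- A reader might infer that Cohort 21 could drop to 50 mg because Table 4 lists nothing below 150 mg. Section 4.3.2 calls 150 mg two levels below 250 mg, so the ladder steps by 50 mg across schedules and the next level down is 100 mg.
- A reader might infer that a hold rule makes the azole PK comparison impossible. With restart on azole completion and an effective voruciclib half-life of 24 to 36 hours (4.3.2.2), some overlap in exposure can occur at either end of a hold.
- A reader might take the two earlier lung cases as a guide to how often Grade 2 arises. They were on continuous dosing and their grades are not given.

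**Conclusion.** Both conflicts are real, sit in current operative text, and have no precedence rule. For azoles, the rule followed in the open cohorts separates replaced from evaluable once a hold costs 4 of 12 or 5 of 19 doses. Reduction never falls below the threshold at 200 mg or above, and in Cohort 21 it does so only beyond 14 of 19 days. This reads 75% as planned milligrams and assumes no other missed doses; at 200 mg with every dose reduced there is no margin. For a qualifying Grade 2 pneumonitis, the choice is between one DLT and none, and between stopping and possible re-exposure.

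The documents do not show how often either situation arises, nor that any completed cohort was misjudged. The point should be fixed because it touches safety instructions and DLT counting, and the remedy is cheap.

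**What to change.** 1. State one azole rule, with one restart time, in both 4.14.1 and 4.15. Either limit the 4.14.1 hold to the 50 mg levels, or take azoles out of the 4.15 reduction sentence (leaving it for other strong CYP3A4 inhibitors) and revise or drop the azole PK comparison in 9.14.2. The choice is a clinical pharmacology decision for the sponsor.
2. State that one level below Cohort 21 is 100 mg. Under either choice the 4.15 reduction still applies there for other strong CYP3A4 inhibitors.
3. Reword the Grade 2 row of Table 12 so that voruciclib is held during work-up and stopped for good on confirmation, as the 4.11 text requires.

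The cost is protocol wording and a memo to sites. Design and sample size do not change. If the hold is kept, the 9.14.2 revision is a small change to a planned analysis.

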4.14.2. Procedures and Surgery

The extent to which voruciclib may affect wound healing, enhance the risk of infection, or increase the risk of bleeding is unknown. Considering parameters such as ANC, platelet count, and PT/aPTT, Investigators may use clinical discretion in deciding whether to interrupt study therapy before and after surgery or other invasive procedures.

4.14.3. Concomitant Medications with Venetoclax – Cautions and Prohibitions

Drugs prohibited according to the [Venclexta \[US Prescribing Information\] Rev 2022](#) (PI) are not permitted in patients enrolled in venetoclax combination cohorts. Per the Venclexta US PI, concomitant use of venetoclax with strong CYP3A inhibitors (e.g., posaconazole) at initiation and during the ramp-up period is contraindicated but allowed for AML with dose reduction (Table 13). Subjects administered prohibited drugs (e.g., azoles) during the screening period must undergo a wash out period (at least 4 half-lives of the prohibited drug) prior to starting Day 1 dosing. For subjects who complete the ramp-up phase and are on a steady daily dose of venetoclax, the venetoclax dose should be reduced by at least 75% when used concomitantly with strong CYP3A inhibitors (e.g., posaconazole). Moderate CYP3A and P-gp inhibitors can be used with venetoclax dose reduction of 50%.

Table 13: Management of Potential Venetoclax Interactions with CYP3A and P-gp Inhibitors

Coadministered Drug	Venetoclax Initiation and Ramp-Up Phase		Steady Daily Dose (After Ramp-Up Phase)
	CLL/SLL	Contraindicated	
Posaconazole	CLL/SLL	Contraindicated	Reduce venetoclax dose to 70mg
	AML	Day 1 – 10 mg Day 2 – 20 mg Day 3 – 50 mg Day 4 – 70 mg	
Other strong CYP3A inhibitor	CLL/SLL	Contraindicated	Reduce venetoclax dose to 100mg
	AML	Day 1 – 10 mg Day 2 – 20 mg Day 3 – 50 mg Day 4 – 100 mg	

Coadministered Drug	Venetoclax Initiation and Ramp-Up Phase	Steady Daily Dose (After Ramp-Up Phase)
Moderate CYP3A inhibitor	Reduce venetoclax dose by at least 50%	
P-gp inhibitor		

Avoid concomitant use of venetoclax with a P-gp substrate. If a concomitant use is unavoidable, separate dosing of the P-gp substrate by at least 6 hours before venetoclax.

4.15. CYP3A4 and P-gp Inhibition Potential of Voruciclib

In in vitro studies, voruciclib was found to inhibit CYP3A4 (testosterone 6 β -hydroxylase activity but not midazolam 1'-hydroxylase activity). Nevertheless, an assessment of voruciclib CYP3A4 inhibition potential was performed using preliminary estimates of enzyme inhibition parameters in a static mechanistic model, and it was estimated that concomitant administration of voruciclib (100 mg dose) and midazolam, a sensitive and specific CYP3A4 substrate widely used in clinical drug-drug interaction studies, may result in approximately 2.5-fold increase in midazolam exposure.

Based on in vitro studies, voruciclib may be a P-gp inhibitor with an IC₅₀ value of 50 μ M; however, the clinical relevance of this finding is not known. The P-gp inhibition potential of voruciclib was assessed according to FDA guidance. At the 100 mg dose level, the ratio of gut concentration to IC₅₀ (I_{gut}/IC₅₀) was estimated to be 17 (0.4 mg/mL divided by 0.024 mg/mL) which is only slightly greater than the threshold value of 10, indicating that the potential for intestinal P-gp inhibition after a voruciclib oral dose of 100 mg is low. Additionally, venetoclax and voruciclib administration will be separated by at least 2 hours (venetoclax will be administered before voruciclib) to further minimize the effect of intestinal P-gp inhibition by voruciclib on venetoclax exposure.

Thus, for the combined therapy portion of the study, at the proposed starting dose of 50 mg of voruciclib, based on in vitro CYP3A4 and P-gp inhibition data presented above, an increase in venetoclax exposure may be observed. [Note that a daily dose of venetoclax above 800 mg has been used in AML without DLTs ([Konopleva 2016](#)).] Therefore, during the period of coadministration with voruciclib, the dose of venetoclax is limited to 200 mg. When administered as a single agent (i.e., on Day 22 through Day 28 with no voruciclib co-administered) the venetoclax dose is 400 mg, consistent with the [Venclexta \[US Prescribing Information\] Rev 2022](#). The summary of the sensitive cytochrome P450 substrates can be found in [Appendix 7](#).

For the combination cohorts on IS_{2w,2w} (Amendment 11), the starting dose of voruciclib in Cohort 12 is 50 mg QOD, which will further reduce voruciclib exposure to account for potential increases (if any) in bioavailability of the new malonate tablet formulation during the exposure cycles. Dosing in Cohort 13 (50 mg QD) will commence only after the safety of QOD dosing of voruciclib with venetoclax in Cohort 12 is established.

For the first two dose levels (50 mg QOD and 50 mg QD), for which voruciclib dose reduction is not possible, voruciclib will be temporarily stopped if the subject requires treatment with an azole antifungal due to the potential of drug-drug interactions and increase exposure to voruciclib. Subjects who recover from the infection can restart voruciclib after the last dose of the azole antifungal (after at least 5 times the half-life of the agent). For subjects receiving

voruciclib at or above 100 mg, a dose reduction by 1 dose level will be required for concomitant treatment with an azole or other strong CYP3A4 inhibitor.

4.16. Impact of COVID-19 on Study Procedures/Visits

MEI Pharma requires the subject to attend the Cycle 1 Day 1 visit on-site; however, if subsequent on-site visits are not possible, study visits during the treatment period may be conducted remotely if a subject is unable to visit a study site due to COVID-19. In this situation, study drug may be shipped directly to a subject if this is deemed appropriate by the Investigator and is acceptable per institutional guidelines and local regulations. If any study visits during the treatment period are conducted via telephone or a tele-health platform, this will be documented in the source file and any missed visit procedures will be recorded as protocol deviations.

4.17. Removal of Subjects from Study

Subjects will be removed from the study for any of the following reasons:

- Withdrawal of consent
- Investigator deems removal to be in the subject's best interest
- Subject is lost to follow-up
- Termination of study by sponsor

5. VORUCICLIB ADMINISTRATION

5.1. Preparation and Administration of Voruciclib

Voruciclib is provided as 50 mg and 100 mg capsules or tablets (requiring no preparation prior to administration) and is dosed on a milligram (mg) basis with no adjustment in dosing based on subject weight. It is recommended that voruciclib be taken in the morning. Voruciclib is to be administered orally once a day on dosing days.

- Monotherapy cohorts: voruciclib is to be taken on an empty stomach at least 1 hour prior to food or 2 hours after food at the same time each day.
- Combination voruciclib + venetoclax cohorts: subjects should take venetoclax with a meal and water, and then take voruciclib (malonate salt tablets) at least 2 hours later (e.g., meal completed at 8 a.m. with venetoclax, dose of voruciclib taken after 10:00 a.m.).

Note that voruciclib is only to be taken on dosing days in the monotherapy IS regimens (i.e., on Days 1 through 14 of the 28-day cycle on the IS_{2w,2w}, and on Days 1 through 7 only in the 28-day cycle on the IS_{1w,3w}). Dosing days for voruciclib when given in combination with venetoclax are defined in [Table 5](#) for IS_{2w,2w}, and in [Table 6](#) for IS_{3w,1w}.

If a dose is missed it may be taken up to 12 hours after the specified time. After 12 hours the dose should be omitted. If a subject vomits after taking voruciclib, no replacement dose will be given.

